7.1.1.2 Expected Adverse Events using Hydroxychloroquine

Blood and lymphatic system disorders	Bone marrow depression, anemia,
	aplastic anemia, agranulocytosis,
	leucopenia, thrombocytopenia.
Cardiac disorders	Cardiomyopathy, which may result
	in cardiac failure and in some cases
	a fatal outcome. Chronic toxicity
	should be considered when
	conduction disorders (bundle branch
	block/ atrioventricular heart block)
	as well as biventricular hypertrophy
	are found. Drug discontinuation may
	lead to recovery.
Ear and labyrinth disorders	Vertigo, tinnitus. Hearing loss
	including cases of irreversible
	hearing loss.
Eye disorders	Common: Blurring of vision due to a

	disturbance of accommodation which is dose dependent and
	reversible.
	Uncommon: Maculopathies which may be irreversible. Retinopathy with changes in pigmentation and visual field defects. In its early form it appears reversible upon discontinuation of the drug. If allowed to develop however, there may be a risk of progression even after treatment withdrawal. Patients with retinal changes may be asymptomatic initially, or may have scotomatous vision with paracentral, pericentral ring types, temporal scotomas, abnormal colour visions, reduction in visual acuity, night blindness, difficulty reading and skipping words. Corneal changes including edema and opacities. They are either symptomless or may cause disturbances such as halos around lights especially at night, blurring of vision or photophobia. They may be transient or are reversible upon
	discontinuation of therapy. Macular degeneration which may be
	irreversible.
Gastrointestinal disorders	Very common: Abdominal pain, nausea
	Common: Diarrhea, vomiting. These symptoms usually resolve immediately upon reducing the dose or upon stopping the treatment.
Hepatobiliary disorders	Uncommon: Abnormal liver
	function tests, fulminant hepatic
T	failure.
Immune system disorders	Urticaria, angioedema,
Metabolism and nutrition disorders	bronchospasm.
Metabolishi and nutrition disorders	Common: Anorexia (usually resolves immediately upon reducing
	resorves infinediately upon reducing

	the dose or upon stopping the
	treatment). Hypoglycemia. May
	exacerbate porphyria.
Musculoskeletal and connective tissue	Uncommon: Sensory motor
Widschioskeitetal and connective tissue	disorders.
	disorders.
	Not known: Skeletal muscle palsies
	or skeletal muscle myopathy.
	Depression of tendon reflexes,
	abnormal results of nerve
	conduction tests. Myopathy may be
	reversible after drug discontinuation,
	but recovery may take many months.
Nervous system disorders	Common: Headache
The rous system disorders	Common. Headache
	Uncommon: Dizziness.
	Chedimion. Bizzmess.
	Not known: Convulsions.
	Extrapyramidal reactions such as:
	akathisia, dystonia, dyskinesia, gait
	disturbance, tremor.
Psychiatric disorders	Common: Affect lability.
	Uncommon: Nervousness Not
	known: Psychosis, suicidal behavior.
Skin and subcutaneous tissue disorders	Common: Skin rash, pruritus
	Uncommon: Pigmentary changes in
	skin and mucous membranes,
	bleaching of hair, alopecia. These
	usually resolve readily upon
	cessation of therapy.
	Not known: Bullous eruptions
	(including urticarial, morbilliform,
	lichenoid, maculopapular, purpuric,
	erythema annulare centrifugum),
	toxic epidermal necrolysis, erythema
	multiforme, Stevens-Johnson
	syndrome, Drug Rash with
	Eosinophilia and Systemic
	Symptoms (DRESS syndrome),
	photosensitivity, exfoliative
	dermatitis, acute generalized
	exanthematous pustulosis (AGEP).

ACED has to be distinguished from
AGEP has to be distinguished from
psoriasis, although
hydroxychlorquine may precipitate
attacks of psoriasis. It may be
associated with fever and
hyperleukocytosis. Outcome is
usually favorable after
discontinuation of drug.

7.2 Adverse Event Characteristics

• CTCAE term (AE description) and grade: The descriptions and grading scales found in the revised NCI Common Terminology Criteria for Adverse Events (CTCAE) version 4.0 will be utilized for AE reporting. All appropriate treatment areas should have access to a copy of the CTCAE version 4.0. A copy of the CTCAE version 4.0 can be downloaded from the CTEP web site http://ctep.cancer.gov/protocolDevelopment/electronic_applications/ctc.htm.

- For expedited reporting purposes only:
 - o AEs for the agent that do not require expedited reporting are defined in Section 7.1.
- **Attribution** of the AE:
 - Definite The AE *is clearly related* to the study treatment.
 - Probable The AE *is likely related* to the study treatment.
 - Possible The AE *may be related* to the study treatment.
 - Unlikely The AE *is doubtfully related* to the study treatment.
 - Unrelated The AE *is clearly NOT related* to the study treatment.

Associated with the use of the *drug/biologic:* There is a reasonable possibility that the experience may have been caused by the drug/biologic.

Life threatening adverse *drug/biologic* **experience:** Any adverse drug/biologic experience that places the subject, in the view of the investigator, at immediate risk of death from the reaction as it occurred.

Serious adverse *drug/biologic* **experience:** Any event is an AE occurring at any dose that results in any of the following outcomes:

- Death
- A life-threatening adverse event (The patient was, in the view of the Investigator, at immediate risk of death from the event as it occurred. It does not mean that the event, had it occurred in a more severe form, might have caused death)Inpatient hospitalization or prolongation of existing hospitalization for ≥ 24 hours. If a complication prolongs hospitalization or fulfills any other serious criteria, the event is serious. Hospitalization for elective treatment of a pre-existing condition that did not worsen from baseline is not

- considered to be an AE)
- A persistent or significant incapacity or substantial disruption of the ability to conduct normal life functions. This definition is not intended to include experiences of relatively minor medical significance such as uncomplicated headache, nausea, vomiting, diarrhea, influenza, accidental trauma (i.e., sprained ankle) that may interfere or prevent everyday life functions but do not constitute a substantial disruption).
- A congenital anomaly/birth defect
- Important Medical Events (IME) that may not result in death, be life threatening, or require hospitalization may be considered serious when, based upon medical judgment, they may jeopardize the patient or subject and may require medical or surgical intervention to prevent one of the outcomes listed in this definition. (Examples include allergic bronchospasm requiring intensive treatment in an emergency room or at home, blood dyscrasias or convulsions that do not result in hospitalization or the development of drug dependency or drug abuse)

Any SAE occurring after the patient has provided informed consent and until 4 weeks after the patient has stopped study participation must be reported. This includes the phase in which the study protocol interferes with the standard medical treatment given to a patient (e.g. treatment withdrawal during screening phase, change in treatment to a fixed dose of concomitant medication). Serious adverse events occurring more than 4 weeks after study discontinuation need only be reported if a relationship to study drug [is suspected.

Unexpected adverse *drug/biologic* **experience:** Any adverse drug/biologic experience, the nature, frequency, or severity of which is not consistent with the product monograph, or not consistent with the risk information described above as a protocol-specific expected adverse event (see Section 7.1.1 "Expected Adverse Events and Protocol-Specific Expedited Adverse Event Reporting Exclusions", above).

7.3 Serious Adverse Event Reporting

7.3.1 Sponsor Notification

Any serious adverse event must be reported to the Central Office within 24 hours of the Investigator at the site learning of the event by a completed SAE form. The adverse event must be completely described in the case report form.

The Princess Margaret Cancer Centre DDP Clinical Trials Group will provide expedited reports of on-study SAEs to Health Canada for those events which meet regulatory requirements for expedited reporting, i.e. events which are BOTH serious AND unexpected (as determined by reference to the Investigator Brochure), AND which are thought to be related to protocol treatment (or for which a causal relationship with protocol treatment cannot be ruled out).

All adverse signs and symptoms which occur during or following the course of drug administration must be reported in detail on the subject's case report form. This description is to include the nature of the sign or symptom, time of onset in relation to drug application, duration, severity, and

possible relationship to drug, required therapy, and outcome. The subject should be followed until the adverse reaction is resolved, or until in the opinion of the Principal Investigator, reversal of the reaction is not likely to occur.

7.3.2 SAE Follow-up

Follow-up SAE reports is subject to the same timelines as the initial report, and is sent to the same parties to whom the original Serious Adverse Event Form was sent. A new serious adverse event form is completed for the follow-up, stating that this is a follow-up to the previously reported serious adverse event and giving the date of the original report. Each re-occurrence, complication or progression of the original event should be reported as a follow-up to that event. The follow-up information should describe whether the event has resolved or continues, if and how it was treated, and whether the patient continued or discontinued study participation.

7.3.3 REB Notification of SAEs

Investigators must notify their Research Ethics Boards (according to their local REB policies) and file the report in their study files. Documentation as outlined below must be maintained for reportable SAEs. Documentation that serious adverse events (SAEs) have been reported to REB must be forwarded to the DDP and kept on file at the Centre. Documentation can be any of the following:

- letter or email from the REB acknowledging receipt
- stamp from the REB, signed and dated by REB chair, acknowledging receipt
- letter or email demonstrating the SAE was sent to the REB

7.3.4 Health Canada SAE Reporting

All serious, unexpected adverse drug reactions must also be reported by the Central Office to Health Canada within 15 days if the reaction is neither fatal nor life threatening, and within 7 days if the reaction is fatal or life threatening.

As the sponsor of this study in Canada, the Principal Investigator for this study will be responsible for reporting all serious unexpected adverse events to Health Canada.

7.4 Routine Adverse Event Reporting

For abnormal laboratory values, it is the responsibility of the Principal Investigator to assess the clinical significance of each abnormality. Only abnormal laboratory values that can be assessed for grade using CTCAE version 4 will be documented. The Investigator will determine whether abnormal laboratory values are considered clinically significant and represent AEs based on their medical judgment.

Data on all adverse experiences/toxicities regardless of seriousness or attribution must be collected in source and CRFs for documentation purposes only.

Clinical Laboratory Abnormalities:

All abnormal and clinically significant laboratory values should be captured on source documentation and assessed for clinical significance by the Investigator at the site. This assessment of clinical significance is to be documented in physician dictation. Only abnormal laboratory values deemed clinically significant and are gradeable per CTCAE version 4.0 should be listed as AEs in source and the CRFs. All clinically significant abnormal laboratory results will be followed up until the related AE resolves, returns to < grade 1 or baseline value in the follow-up period. Additionally, laboratory abnormalities resulting in an intervention or dose modification are considered to be clinically significant.

7.5 Documentation of Adverse Events

All AEs must be captured in the source documents, as well as reported in *electronic document capture (EDC) system*. AEs reported using SAE forms must also be reported in *EDC system*.

All serious and non-serious AEs occurring from the start of study medication administration to the end of study drug administration visit must be recorded as AEs on the CRF. Investigators, sub-investigators, and delegated individuals should review all documentation (e.g., hospital progress notes, laboratory, or diagnostic reports) relative to the event being reported.

7.6 Follow-Up of AEs and SAEs

SAEs and AEs should be followed for 12 weeks after the last dosing of study drug/biologic or until they are resolved (return to normal or baseline values), stabilized, improve to Grade 1, or the patient is lost to follow-up and cannot be contacted. Additional investigations (*e.g.*, laboratory tests, diagnostic procedures, or consultation with other healthcare professionals) may be required to completely investigate the nature and/or causality of an AE or SAE. If the patient dies during the study or within 12 weeks following the last dose of study medication, any postmortem findings (including histopathology) should be provided to the Sponsor. CRF data should be updated with any new information as appropriate.

7.7 Pregnancy

Any pregnancy of a study subject or of a study subject's partner that occurs during study participation should be reported for pregnancies that occur up to 30 days after the last dose of study medication. If the study subject is the father, then two SAE forms should be completed, one for the father and the other for the mother and neonate. The pregnancy should be followed up to determine outcome, including spontaneous or voluntary termination, details of birth, and the presence or absence of any birth defects, congenital abnormalities or maternal and newborn complications.

7.8 Investigator Notifications

As both drugs are available as commercial products, the Sponsor-Investigator will not be receiving any Investigator Notifications throughout the lifetime of this study.

7.9 Data Safety and Monitoring Board

A Data Safety and Monitoring Board, an independent group of experts, will be reviewing the data from this research throughout the study to see if there are unexpected or more serious side effects than described in the consent. For this trial, the Drug Development Program DSMB will be responsible for these tasks.

8. PHARMACEUTICAL INFORMATION

8.1 Investigational Agents

8.1.1 Itraconazole

Intraconazole Manufacturing

Janssen Inc. manufactures itraconazole for clinical use.

Intraconazole Packaging and Labeling

Itraconazole will be packaged as per commercial standards. Labels will be affixed to the packaging containing the following information in English and French:

Protocol Code:

Investigational Drug name and formulation (mg)

Lot Number:

Contents: Number of capsules (XX capsules)

Store at XX Temperature (XX °C)

Investigational drug. To be used by qualified investigators only.

Sponsor-Investigator: [name]

Investigational agent Handling and Storage

Investigational agent will be stored under secure (with limited access), and temperature-controlled conditions for the duration of the study. Investigational agent bottles will be stored at ambient temperature (i.e.15-30°C) in an area accessible only to authorized staff. Patients will be asked to store their one-month supply of drug at ambient temperature. Study drug inventory forms will be kept by the Investigator, or designee.

Intraconazole Ordering and Shipping

Itraconazole will be purchased by each site from commercial supply.

Study medication should only be dispensed once a patient has (1) signed an informed consent form (ICF), (2) met all eligibility criteria for entry into the study, (3) completed all screening and continuing eligibility requirements, and (4) been assigned a patient identification number.

Agent Accountability

The Investigator is responsible for study medication accountability, reconciliation, and record maintenance. In accordance with all applicable regulatory requirements, the Investigator or designated study personnel must maintain study medication accountability records throughout the study.

The accountability records maintained during the study will be used to support patient dosing data. Site personnel are responsible for reconciling and resolving discrepancies in study medication accountability.

Missing study medication must be recorded along with an explanation of the discrepancy.

Agent Inventory Records

The investigator, or a responsible party designated by the investigator, must maintain a careful record of the inventory and disposition of all agents received using their site-specific Drug Accountability Record Form (DARF).

Description: Itraconazole is a synthetic triazole antifungal agent.

Physical Characteristics: A white or almost white powder, practically insoluble in water, freely soluble in methylene chloride, sparingly soluble in tetrahydrofuran, very slightly soluble in alcohol.

Product description: Itraconazole is available as capsules containing 100 mg of itraconazole, with a blue opaque cap and pink transparent body. They are supplied in unit-dose blister packs or HDPE bottles.

Storage requirements: This medicinal product does not require any special temperature storage conditions. Store in the original package in order to protect from light and moisture. Shelf life: 30 months.

Route of administration: Oral administration and should be taken with food. Capsules should be swallowed whole.

8.1.2 Hydroxychloroquine

Hydroxychloroquine Manufacturing

Apotex Inc. manufactures hydroxychloroquine for clinical use.

Hydroxychloroquine Packaging and Labeling

Hydroxychloroquine will be packaged as per commercial standards. Labels will be affixed to the packaging. Study drug labeling will contain the following information in English and French:

Protocol Code:

Investigational Drug name and formulation (mg)

Lot Number:

Contents: Number of tablets (XX tablets)

Store at XX Temperature (XX °C)

Investigational drug. To be used by qualified investigators only.

Sponsor-Investigator: [name]

Hydroxychloroquine Handling and Storage

Investigational agent will be stored under secure (with limited access), and temperature-controlled conditions for the duration of the study. Investigational agent bottles will be stored at ambient temperature (i.e.15-25°C) in an area accessible only to authorized staff. Patients will be asked to store their one-month supply of drug at ambient temperature. Study drug inventory forms will be kept by the Investigator, or designee.

Hydroxychloroquine Ordering and Shipping

Hydroxychloroquine will be purchased by each study site from commercial supply., and shipped directly to each site.

Study medication should only be dispensed once a patient has (1) signed an informed consent form (ICF), (2) met all eligibility criteria for entry into the study, (3) completed all screening and continuing eligibility requirements, and (4) been assigned a patient identification number.

Agent Accountability

The Investigator is responsible for study medication accountability, reconciliation, and record maintenance. In accordance with all applicable regulatory requirements, the Investigator or designated study personnel must maintain study medication accountability records throughout the study.

The accountability records maintained during the study will be used to support patient dosing data. Site personnel are responsible for reconciling and resolving discrepancies in study medication accountability.

Missing study medication must be recorded along with an explanation of the discrepancy.

Agent Inventory Records

The investigator, or a responsible party designated by the investigator, must maintain a careful record of the inventory and disposition of all agents received using their site-specific Drug Accountability Record Form (DARF).

Description: Hydroxychloroquine is an antimalarial drug derived from chloroquine.

Product description: Each white, capsule-shaped, biconvex film-coated tablet engraved 'APO' on one side and 'HCQ 200' on the other contains hydroxychloroquine sulfate 200 mg. Available in bottles of 100 and 500 tablets, unit dose packages of 30 and 100.

Storage requirements: Store at room temperature (15°C -30°C).

Route of administration: Oral administration should be taken with food or milk. Do not crush pills.

9. CORRELATIVE, AND SPECIAL STUDIES

9.1 Laboratory Correlative Studies

Clinical response to treatment as defined by the main drug treatment clinical protocol will be compiled and results of biomarker analysis from "responders" and "non-responders" will be compared. These correlative studies are exploratory in nature and will be used in the design of future larger studies.

Laboratories from the following institutions will be involved in correlatives analysis:

- Princess Margaret Cancer Centre Labs, Toronto, Ontario;
- University Health Network Lab, Toronto, Ontario;
- Ontario Institute for Cancer Research (OICR), Toronto, Ontario;
- Princess Margaret, OICR Translational Genomic Labs, Toronto, Ontario.

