Target lesions. All measurable lesions up to a maximum of 2 lesions per organ and 5 lesions in total, representative of all involved organs, should be identified as **target lesions** and recorded and measured at baseline. Target lesions should be selected on the basis of their size (lesions with the longest diameter), be representative of all involved organs, but in addition should be those that lend themselves to reproducible repeated measurements. It may be the case that, on occasion, the largest lesion does not lend itself to reproducible measurement in which circumstance the next largest lesion which can be measured reproducibly should be selected. A sum of the diameters (longest for non-nodal lesions, short axis for nodal lesions) for all target lesions will be calculated and reported as the baseline sum diameters. If lymph nodes are to be included in the sum, then only the short axis is added into the sum. The baseline sum diameters will be used as reference to further characterize any objective tumor regression in the measurable dimension of the disease.

Non-target lesions. All other lesions (or sites of disease) including any measurable lesions over and above the 5 target lesions should be identified as **non-target lesions** and should also be recorded at baseline. Measurements of these lesions are not required, but the presence, absence, or in rare cases unequivocal progression of each should be noted throughout follow-up.

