11.1.4.1 Evaluation of Target Lesions

Complete Response (CR): Disappearance of all target lesions. Any pathological lymph nodes (whether target or non-target) must have reduction in short axis to <10 mm.

Partial Response (PR): At least a 30% decrease in the sum of the diameters of target lesions, taking as reference the baseline sum diameters.

Progressive Disease (PD): At least a 20% increase in the sum of the diameters of target lesions, taking as reference the smallest sum on study (this includes the baseline sum if that is the smallest on study). In addition to the relative increase of 20%, the sum must also demonstrate an absolute increase of at least 5 mm. (Note: the appearance of one or more new lesions is also considered progressions).

Stable Disease (SD): Neither sufficient shrinkage to qualify for PR nor sufficient increase to qualify for PD, taking as reference the smallest sum diameters while on study, including baseline. Note that patients are not able to go from PR to SD.

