11.1.7 Overall Response Rate

The ORR is defined as the proportion of patients achieving complete response (CR) or PR as assessed by the Investigator per RECIST (v.1.1).

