13.2 Sample Size/Accrual Rate

The sample size will be a maximum of 52 patients. This will encompass between 6 and 18 on phase I and 34 on for the phase II component.

Phase II sample size:

Stage 1 of accrual: 9 response evaluable patients will be entered in the first stage. Using response hypotheses of H_0 <15 % and H_a >35%, we would reject the drug at the end of the first stage of accrual if no objective responses were seen. Otherwise, an additional 25 patients will be accrued. Patients treated at RP2D in the phase 1 part of the study will be considered for the statistical analysis of the phase 2 stage 1. A total (between phase 1 and phase 2 stage 1) of 9 response evaluable patients treated at RP2D are required.

Stage 2 of accrual: An additional 25 patients will be accrued. We would accept the drug as active if 8 or more objective responses are observed from 25 patients accrued.

Significance level and power: The procedure described above test the null hypothesis that the response rate is 15% versus alternating hypotheses that the response rate is 35%. The significance level (*i.e.*, the probability of rejecting H0 when it is true) is α =0.05 and the power (*i.e.*, the probability of deciding the regimen is active) is 0.81 when true response rate is 20%. The expected sample size with this design is 19 when the null hypothesis is true and 25 when the alternative hypothesis is true.

Accrual and Duration of Study

The estimated accrual for this study is 2-4 patients a month. Thus, patient accrual is expected to be completed within 12-18 months. Additional time is required to allow the response data to mature.

All of the patients registered in the study will be accounted for. The number of patients who were not evaluable, who died or withdrew before treatment began will be specified. The distribution of follow-up time will be described and the number of patients lost to follow-up will be given.

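### Section 9.1 names only a responder versus non-responder split for relating biomarkers to outcome; percent change in target-lesion size, already collected, should be named beside it

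*Protocol*

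**What the plan says.** Protocol section 9.1 introduces the correlative work with "Clinical response to treatment as defined by the main drug treatment clinical protocol will be compiled" and then states that "results of biomarker analysis from 'responders' and 'non-responders' will be compared". It describes the status of this work as follows: "These correlative studies are exploratory in nature and will be used in the design of future larger studies".

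The response behind the split is defined in 11.1.7 as the "proportion of patients achieving complete response (CR) or PR as assessed by the Investigator per RECIST (v.1.1"). Under 11.1.4.1, partial response requires "At least a 30% decrease in the sum of the diameters of target lesions, taking as reference the baseline sum diameters". The measurement underneath is continuous and recorded. Section 11.1.2 says "The baseline sum diameters will be used as reference to further characterize any objective tumor regression in the measurable dimension of the disease", section 11.1 re-evaluates disease every 8 weeks, and measurable disease is an entry criterion (3.1.4).

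The response rates come from 13.2: "The procedure described above test the null hypothesis that the response rate is 15% versus alternating hypotheses that the response rate is 35"%. The same section sets 9 response-evaluable patients for stage 1, rejects the regimen if none of them responds, and otherwise adds 25.

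Section 13.4, headed as the analysis of secondary endpoints, allows Pearson or Spearman correlation, t-tests, rank sum tests and logistic regression for associations between variables. It mentions neither biomarkers nor change in tumour size.

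**The concern.** Percent change in the sum of target-lesion diameters can be derived for every patient with a follow-up measurement. Replacing it by a yes/no at 30% shrinkage treats a patient with 29% shrinkage like one with growth. At the response rates used for planning, the two groups are also very uneven. If biomarker level tracks shrinkage, a test of two unequal groups has clearly less power than a correlation with the measured change.

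The design adds a second difficulty. The early stop is triggered by the absence of responders, which is exactly when a responder comparison has nothing to compare.

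At stake is how much the paired biopsies can say about which patients benefit, since the results are meant to inform later, larger studies. No confirmatory conclusion of this trial depends on it.

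**Working it through.** The protocol states no power, sample size or effect size for the biomarker comparison, so there is no planned figure to reproduce.

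**Inputs from the protocol.** Response rates p of 15% and 35%; 9 patients in stage 1; 9 + 25 = 34 in both stages (13.2).

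**Assumptions.** Two-sided 5% test, in line with the 95% intervals of 13.4. Biomarker and percent change are bivariate normal with correlation 0.3 to 0.6. All 34 patients have a usable biomarker and a follow-up measurement; fewer would lower power for both methods.

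**1. Group sizes at n = 34.** 34 × 0.15 = 5.1, so about 5 against 29. 34 × 0.35 = 11.9, so about 12 against 22.

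**2. Chance of no responder.** P(0 of n) = (1 − p)^n.
- n = 9, p = 15%: 0.85^9 = 0.232. At most one responder: 0.232 + 9 × 0.15 × 0.85^8 = 0.232 + 0.368 = 0.60.
- n = 9, p = 35%: 0.65^9 = 0.021.
- n = 34, p = 15%: 0.85^34 = 0.004.

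The problem of an empty group therefore belongs to the stage 1 stop, not to the full cohort.

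**3. Large-sample efficiency of the split.** Under normality it is φ(z)² / [p(1 − p)], where z cuts off the upper fraction p.
- p = 15%: 0.2332² / 0.1275 = 0.43.
- p = 35%: 0.3704² / 0.2275 = 0.60.

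For weak associations the split therefore works as if about 34 × 0.43 ≈ 15 or 34 × 0.60 ≈ 20 patients had been analysed by correlation.

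**4. Simulated power at n = 34.** The outcome is cut so that a fraction p responds. Spearman on percent change is compared with the rank sum test on responder status (6,000 runs per cell).

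| Correlation | Spearman | Split, 15% rate | Split, 35% rate | Loss in points (15% / 35%) |
|---|---|---|---|---|
| 0.3 | 38% | 18% | 25% | 20 / 13 |
| 0.4 | 62% | 30% | 42% | 32 / 20 |
| 0.5 | 83% | 45% | 61% | 38 / 22 |
| 0.6 | 95% | 61% | 80% | 34 / 15 |

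Pearson against the t-test (20,000 runs per cell) gives losses of 22, 35, 40 and 33 points at a 15% rate and 15, 22, 22.5 and 14 points at 35%. Outside this range the loss shrinks: 6 to 9 points at correlation 0.2, and 10 points (15% rate) or 1 point (35% rate) at correlation 0.8.

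**5. Dependence on the model (n = 34).** Percent change is given first, then the split at 15% and 35%.
- Correlation 0.5, the 40% with the worst target change tied at worst rank: 78% against 44% and 61%. The gain survives.
- Correlation 0.5, worst rank given to 30% of patients independently of target change, for example progression by new lesions: 28% against 30% and 39%. The gain is gone or reversed.
- Biomarker shifted by 1.2 SD in responders only: 26% against 60% at a 15% rate, and 67% against 85% at 35%. The split wins.

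**6. At n = 9.** Spearman can be computed without responders, but its power is only about 11% to 26% at correlations 0.3 to 0.5.

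**The case against.** The case on the other side has four parts.

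- **The text is not exclusive.** A reader might infer that the protocol limits itself to the split and throws the measured change away. It says neither. Section 13.4 allows correlation in general terms, the work is labelled exploratory, and a statistical analysis plan may say more. This stands. What remains is that 9.1 makes a specific choice and 13.4 does not connect its methods to biomarkers or tumour size.
- **Most correlative work needs no responders.** A reader might infer that a stop at 0 of 9 ends the correlative programme. It does not. The objectives in 1.3 on mechanism, apoptosis, cholesterol and angiogenesis use paired biopsies, and 2.3.6 investigates candidate genes with drop-out screens in patient-derived cell lines. Only the responder comparison fails, and only at the recommended phase 2 dose.
- **Response carries more than target size.** Under 11.1.4.3 it also depends on non-target lesions, new lesions and confirmation. Percent change in target lesions ignores these, and a worst-rank rule to bring them back can remove the gain (step 5). This stands, and is why that rule belongs in a sensitivity analysis.
- **The direction of the gain depends on the model.** If only true responders differ in the biomarker, the split is better. This also stands, so the documents do not support replacing the responder comparison or reducing it to description.

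**Conclusion.** The point holds as a minor one. Section 9.1 names a single way to relate biomarkers to outcome, a RECIST split, while a more informative measure is already collected.

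If the association is roughly monotone in shrinkage (bivariate normal, correlation 0.3 to 0.6), the split costs about 13 to 40 points of power at n = 34. A flat 20 to 40 points might be inferred, but that range belongs to a 15% response rate; at 35% the loss is about 13 to 22. The correlation is an assumption throughout, because the protocol gives none.

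The comparison cannot be computed at the recommended phase 2 dose after a 0 of 9 stop, which has probability 23% at a 15% response rate. Percent change could still be analysed there, but with nine patients it would tell little. The documents support adding the continuous analysis, not swapping one for the other.

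**What to change.** In section 9.1, keep the responder comparison and add wording to this effect:

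> Baseline biomarker level and pre-to-on-treatment change will also be related to best percent change from baseline in the sum of target-lesion diameters, by Spearman correlation; for binary markers such as mutation status, percent change will be compared between marker groups by the Wilcoxon rank sum test. All patients with a follow-up measurement are included. A sensitivity analysis assigns the worst rank to patients with progression by new or non-target lesions, clinical progression or early death.

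This needs no new visits, samples or patients, and the methods are already among those listed in 13.4. The cost is one more exploratory analysis to report and interpret. Where it disagrees with the responder comparison, both should be shown.
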